## **PROTOCOL SUMMARY**

### **1. Background and Rationale**

HIV-related disparities persist among Latinx communities, especially those who are immigrants and sexual minority men (SMM). In 2017, Latinx adults showed HIV rates 3.2 times higher than White adults, and Latinx SMM (LSMM) accounted for 75% of all HIV diagnoses among Latinx adults; 67% of newly diagnosed HIV infections among LSMM were immigrants. Latinx adults, especially those who are immigrants, are diagnosed with HIV (i.e., tested) at a later disease stage, leading to delays in treatment. In addition, only 13.1% of Latinx adults reported pre-exposure prophylaxis (PrEP) use in 2016, compared to 68.7% of White adults. However, of the HIV prevention interventions listed in the CDC's Compendium of Evidence-Based Interventions, only one was developed for LSMM, and none have yet been developed or assessed for PrEP use.

In this study we will integrate HIV prevention strategies into a coping intervention that includes 8-sessions of group cognitive behavioral therapy (CBT) for HIV-negative LSMM that aims to improve adaptive coping responses to discrimination and increase preventive strategies. We hypothesize that the intervention will improve coping responses to discrimination and HIV testing and PrEP use.

### **2. Objectives**

This objectives of this study are to: 1) conduct a randomized controlled trial of a coping intervention that is a culturally congruent CBT group intervention for immigrant LSMM, to test intervention effects on regular HIV testing and PrEP use; 2) examine mechanisms of intervention effects on regular HIV testing and PrEP use, including more effective coping; and 3) conduct a cost-effectiveness analysis of the intervention.

### **3. Study Design**

We will conduct 10 intervention groups and 10 standard of care control groups of about 15 participants each (n=300). After participants complete the baseline assessment, we will randomize them into the intervention or standard of care control groups. Participants will complete audio computer-assisted interviews at baseline, and 4, 8, and 12-month follow-ups. The intervention will last 8 weeks (7 sessions of content plus a "graduation").

The proposed study is a partnership among academic researchers and stakeholders of Los Angeles County (LAC) Latinx and HIV-affected communities. Bienestar will be a full and equal partner throughout the research. Bienestar, LAC's largest Latinx-serving HIV service organization, provides services (e.g., case management, substance use, mental health) in 7 offices in LAC to people living with HIV and HIV prevention to those at risk.

Participants in the standard of care control group will be provided with information about an ongoing weekly two-hour open wellness-oriented support group available to all clients at Bienestar. The program includes an open support group; psychoeducation on wellness topics (e.g., HIV prevention, sexuality, spirituality, self-esteem, other health promotion topics); and social and cultural activities with food, art, and music.

## 4. Methods

### *Screening/Recruitment*

As in our prior pilot test, we will recruit participants via fliers left at the clinic at which the intervention will be conducted (Bienestar) and other community-based organizations and clinic (in waiting areas, on bulletin boards), fliers disseminated by Bienestar staff (e.g., HIV testing counselors, substance use counselors) to clients, and online advertisements. We will hold brief information sessions at client and staff gatherings. We will hire a research assistant from the local community for recruitment and tracking who is well-connected with the local HIV population and familiar with local HIV services for Latinx adults. Members of the Community Advisory Committee will also be asked to assist with recruitment.

Participants will be eligible if they are  $\geq 18$  years-old, biologically male at birth; identify as male; identify as a Latino immigrant; report having sex with men in the past 12 months; report HIV-negative or unknown serostatus; anticipate being available for the next 12 months to attend study visits; and able to interact and communicate in spoken Spanish or English. The latter two criteria will be important to ensure that individuals will be able to actively participate in the intervention sessions.

Women, including transgender women, will not be eligible because they face discrimination regarding gender/gender identity that would necessitate a differently tailored intervention with additional content and components that the present intervention lacks.

### *Procedures*

The coping intervention will be conducted in groups and situated in a trusted community venue. The intervention was developed with, and will be delivered by, credible community stakeholders knowledgeable about SMM culture—individuals not viewed as authority figures or part of the medical system. The intervention will be led by an expert facilitator (with experience leading groups) and a peer co-facilitator (with experience working with SMM). Both facilitators are matched on client ethnicity to increase credibility and trust.

The intervention will utilize several counseling techniques:

*Psychoeducation:* All participants will receive basic HIV and prevention education. We will raise awareness about disparities and discrimination (e.g., links between discrimination and lack of engagement in medical care) and address medical mistrust. Facilitators will acknowledge historical and current challenges, including discrimination, which lead to mistrust, and mental health, substance use, and poverty (and, if necessary, provide referrals for services). The intervention will also address HIV and sexual orientation stigma in Latinx communities, and how stigma can be a barrier to seeking support, accessing healthcare, and adherence to prevention strategies such as PrEP.

*Cognitive Behavioral Therapy:* CBT aims to empower clients to be their own agents of change, building on existing strengths and skills. CBT involves educating clients about the relations among their thoughts, behaviors, and emotions. Counselors help clients to understand a given problem behavior (e.g., rumination after discrimination) in terms of the chain of events that led to the behavior (a functional analysis/chain analysis) as well as the behavior's consequences. Clients can be guided through a step-by-step, micro-level recounting of thoughts, feelings, and emotions related to a specific event/behavior chain (distal vulnerability factors, proximal prompting events, immediate and longer-term consequences of coping strategies), and they work with the counselor collaboratively to identify problematic 'links' in the chain. Counselors teach clients cognitive and behavioral skills (mindfulness, cognitive restructuring, relaxation) for better coping. Skills are practiced in session, and behavioral self-monitoring and further practice are assigned between sessions to facilitate skills generalization. The counselor teaches clients the utility of having a 'toolbox' of potential strategies to use for different situations, and how to

strategically select a skill that best matches a given problem. Skills are understood and evaluated in the context of clients' values ("It's important to stay healthy") and goals ("I want to get tested regularly for HIV"). CBT is useful in groups because antecedents or consequences of many problem behaviors are interpersonal (e.g., disrupted relationships) and because clients can 'test out' new skills vicariously through the experiences of other group members.

We will administer 4 survey waves: baseline, 4-months post-baseline (shortly after intervention completion), 8-months post-baseline, and 12-months post-baseline. Surveys will be administered at Bienestar using audio computer-assisted self-interviews. Participants will complete the baseline survey before randomization. Participants who drop out of the program will be encouraged to complete all surveys.

To validate self-reports, we will obtain HIPAA consent to obtain medical and administrative records, which we will use to verify HIV status, HIV testing practices, service use, and PrEP use.

For **process evaluation** purposes, we will assess feasibility and acceptability to inform future dissemination efforts. Following implementation science recommendations, we will assess feasibility in terms of: recruitment rate (number recruited per month, of number expected); refusal rates, and intervention session retention. We will assess feasibility of eligibility criteria (sufficient vs. too restrictive) by examining proportion of potential participants screened as ineligible and reasons why. Feasibility will also be assessed with post-session evaluation forms completed by facilitators and the site Co-Investigator (who will listen to all recorded sessions), to assess session flow, areas for improvement (whether some activities need to be changed, shortened, or eliminated), and whether key elements were covered adequately (which will also be used for fidelity). Acceptability, the extent to which people delivering or receiving an intervention consider it to be appropriate, based on anticipated or experienced responses, will be assessed via facilitator and participant post-session evaluation forms, which will ask how much the facilitator and participant liked or did not like the session on Likert scales, and why, in open-ended responses.

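### Participant acceptability rests on post-session forms alone, so never-attenders give no rating, men who stop are under-weighted, and no step asks why they stopped

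*Combined protocol and SAP*

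**What the plan says.** The process-evaluation text in Section 4 (Procedures) defines acceptability as "the extent to which people delivering or receiving an intervention consider it to be appropriate, based on anticipated or experienced responses". It then names one way of measuring it: acceptability "will be assessed via facilitator and participant post-session evaluation forms, which will ask how much the facilitator and participant liked or did not like" each session. Answers are given on Likert scales, with reasons as free text. The unit being rated is the session, and the form follows the session.

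Attendance is covered separately, under feasibility, through "refusal rates, and intervention session retention". For screening, the same text also asks for the reasons men were ineligible. It states no equivalent for men who leave the program.

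Earlier in Procedures the plan schedules a survey at month 4, shortly after the intervention ends, with further waves at months 8 and 12. It adds: "Participants who drop out of the program will be encouraged to complete all surveys". The items in those surveys are not listed.

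**The concern.** A form about a session can be filled in only by someone who was there. Three gaps follow.

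- A man randomized to the intervention who never attends supplies no rating.
- A man who stops rates the sessions he attended, but not the program as a whole, and he is not asked why he stopped.
- When forms are pooled, men count in proportion to the number of sessions they attended, so those who stayed dominate.

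The plan's definition of acceptability includes anticipated as well as experienced responses, so it reaches further than the instrument does. If stopping is related to disliking the program, the pooled rating may be too favourable, and later sessions may look better received only because the less satisfied men have gone. Acceptability is collected to guide dissemination, and reasons for leaving bear directly on how the program should be adapted. Retention counts show how many men left, but not what they thought.

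**Working it through.** **Plan figures.** The documents give no acceptability target, dropout rate or number of scale points, so there is no stated figure to reproduce. Section 3 gives 10 intervention groups of about 15, or about 150 men (20 × 15 = 300 agrees with the stated total). It also gives 8 weeks: seven content sessions and a graduation.

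**Assumptions, for illustration only.** A 5-point scale; men who continue rate 4.5 throughout; men who stop would rate 3.0 throughout; leavers attend the first 2 of 8 meetings; one form per man per meeting attended; a proportion *a* continues.

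**Formulas.**
- Mean over all assigned men: 4.5*a* + 3.0(1 − *a*)
- Leavers' share of forms: *s* = 2(1 − *a*) / [8*a* + 2(1 − *a*)]
- Pooled mean of forms: 4.5 − 1.5*s*
- Overstatement: 1.5 × [(1 − *a*) − *s*]

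**Results.**

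| | 70% continue | 50% continue |
|---|---|---|
| Forms from men who continue | 105 × 8 = 840 | 75 × 8 = 600 |
| Forms from leavers | 45 × 2 = 90 | 75 × 2 = 150 |
| Leavers' share of forms | 90/930 = 0.097 | 150/750 = 0.20 |
| Pooled mean | 4.35 | 4.20 |
| Mean over all assigned | 4.05 | 3.75 |
| Overstatement | 0.30 | 0.45 |

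At 70% continuing, leavers are 30% of the men but supply about 10% of the forms.

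**Apparent trend.** Under the same assumptions the mean for sessions 1–2 is 4.05 and for sessions 3–8 is 4.50, a rise of 0.45 although no man has changed his rating. At 50% continuing the rise is 4.50 − 3.75 = 0.75.

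**Sensitivity** (70% and 50% continuing).
- Rating gap of 1.0 instead of 1.5: about 0.20 and 0.30.
- Rating gap of 0.5: about 0.10 and 0.15.
- No gap: zero. If leavers liked the sessions more, the sign reverses.
- All men who do not continue never attend (*s* = 0, gap 1.5): 1.5 × 0.3 = 0.45 and 1.5 × 0.5 = 0.75. This is the upper end for that gap.
- Forms averaged within each man first: zero among men who attended at least once, if ratings are stable. Never-attenders would still be missing.

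**The case against.** The strongest case against is that a reader might infer more than the text supports, in four ways.

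*That men who stop are never asked.* They are. A man who leaves after session 2 is expected to have completed two forms, each with an open-ended question on what he liked or disliked and why. Only men who attend no session are wholly missing.

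*That acceptability is overstated.* This requires leavers to have liked the program less, and men may leave because of work, moving or other reasons. The documents give no figures from which the size or sign of any bias could be found.

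*That the distortion is 0.45 to 0.75 points at 70% to 50% continuing.* Those values give leavers no weight at all. They apply to a single late session, or if every man who does not continue never attended.

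*That the month-4 survey contains no such item.* The text is a protocol summary and lists no survey content, so this cannot be settled from it. What can be said is that the plan states how acceptability will be measured and names only the forms.

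It is also fair to say that retention is reported in the same evaluation and shows how selective the ratings are; that facilitator forms and the review of recorded sessions do not depend on participants returning; and that no target, test or decision rule rests on acceptability. These points limit the concern but do not remove it: none of these sources records what men who stayed away thought, or why they left.

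**Conclusion.** The concern holds in limited form. On the text, the forms are the only participant measure of acceptability, they weight men by attendance, and no step is described to ask why men stopped. That pooled ratings **may** overstate acceptability is a reasonable inference; that they do is not established. The illustrative 0.30 and 0.45 points depend entirely on the assumed ratings, the assumed continuation and the assumed two sessions attended by leavers, and would be zero without a difference in liking.

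This is a minor, optional improvement to the process evaluation. The primary HIV testing and PrEP analyses are by intention to treat regardless of session attendance (Section 5) and are not affected.

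**What to change.** In the existing month-4 survey, ask every man randomized to the intervention, whatever his attendance, for:

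1. an overall acceptability rating of the program; and
2. his reasons for missing or stopping sessions, where that applies.

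Report this rating alongside the post-session ratings, by number of sessions attended. Show never-attenders separately, because they can report only anticipated views. Give the number of forms behind each session's rating, so that a change across sessions can be read against attrition. The session ratings should be kept: the two measure different things, and the overall rating need not replace them. If the survey already contains such items, the process-evaluation text should say so.

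The cost is a few items at a visit already planned. The drawbacks are a slightly longer survey, some recall error, and continued non-response among dropouts, who are encouraged but not certain to complete it.

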## 5. Statistical Analysis

**Main Analyses.** We hypothesize that the coping intervention will result in higher likelihoods of regular HIV testing and PrEP use, and improved coping with stigma (e.g., reduced internalized stigma). We will perform descriptive statistics and transform outcomes with skewed distributions (log or other as appropriate) to stabilize error variances and reduce outlier influence in regressions. We will select covariates from variables hypothesized on the basis of theory and previous research to predict outcomes, and for which we find support in bivariate baseline analyses (at  $p < .10$ ). We will use intention-to-treat analysis, i.e., analyze participants according to the group to which they were randomized, regardless of session attendance. Aim 1. We will use repeated-measures logistic regression for our primary HIV testing and PrEP dichotomous outcomes. Aim 2. For secondary outcomes (e.g., coping, internalize stigma) on which the coping intervention shows significant effects, to test mediation we will compare: (a) Aim 1 models, adding baseline measures of hypothesized mediators; and (b) the same models as in (a), adding post-intervention measures of hypothesized mediators. We will examine whether including post-intervention mediators in (b) decreases the coefficient for intervention effects on the outcome relative to the corresponding coefficient from (a). We will test interactions between each moderator and intervention group in the models for Aim 1.

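### The primary (Aim 1) model allows for repeated measures within a person but not for delivery in 10 therapy groups, so both primary tests are too liberal if outcomes correlate within those groups

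*Combined protocol and SAP*

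**What the plan says.** Section 3 (Study Design) sets the structure: "We will conduct 10 intervention groups and 10 standard of care control groups of about 15 participants each (n=300"). It randomizes individuals: "After participants complete the baseline assessment, we will randomize them into the intervention or standard of care control groups". The Procedures part of section 4 confirms group delivery: "The coping intervention will be conducted in groups and situated in a trusted community venue". It also presents groups as useful because clients can try "new skills vicariously through the experiences of other group members".

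Section 5 gives one sentence on the primary model: "We will use repeated-measures logistic regression for our primary HIV testing and PrEP dichotomous outcomes". Its intention-to-treat rule is to "analyze participants according to the group to which they were randomized, regardless of session attendance"; there, group means the randomized arm, not the therapy group. The Aim 2 mediation comparison is built on the Aim 1 models, and so are the moderator tests: "We will test interactions between each moderator and intervention group in the models for Aim 1".

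The control arm is described in two ways in section 3. It is counted as 10 groups, but also: "Participants in the standard of care control group will be provided with information about an ongoing weekly two-hour open wellness-oriented support group".

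**The concern.** People who sit in the same room for eight weeks and learn from one another may end up with more similar outcomes than people in different rooms. The two usual forms of a repeated-measures logistic model are a GEE clustered on participant and a mixed model with a participant random intercept. Both treat the 150 people in the intervention arm as independent of one another. With only 10 groups in that arm, any between-group variation is left out of the standard error of the arm comparison.

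This affects both primary outcomes and passes to the mediation and moderator models built on them. Confidence intervals are too narrow whenever the programme works unevenly across groups. Tests exceed their level under a null of zero average effect with group effects that vary. That null matters for any claim beyond these 10 particular groups.

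Repeated measurement makes the problem worse. Averaging over waves reduces person-level noise but does not reduce a group effect that persists.

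**Working it through.** **Plan's own figure.** (10 + 10) groups × 15 = 300, which matches the stated n. The documents give no power calculation to reproduce.

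**Inputs from the documents.** Individual randomization; 10 intervention groups of about 15; 150 per arm (10 × 15); three follow-ups at 4, 8 and 12 months; two binary primary outcomes.

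**Assumed, because not stated.** Two-sided 5%; ICC 0.01 to 0.10; clustering in the intervention arm only; within-person correlation r = 0.5; event rate 0.40 (simulation only); no dropout.

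**Formulas.**
- Design effect in the intervention arm: DE = 1 + 14 × ICC.
- Ratio of true to assumed variance of the arm contrast: R = (DE + 1)/2.
- Actual type I error: 2 × (1 − Φ(1.96/√R)).
- If 10 of 15 attend and only attenders are correlated: DE = (10 × (1 + 9 × ICC) + 5)/15.
- Three waves with a constant group effect: replace ICC by ICC/((1 + 2r)/3), which is 1.5 × ICC at r = 0.5.

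**Example, ICC 0.05.** Single wave: DE = 1.70, R = 1.35, 1.96/√1.35 = 1.687, type I error 9.2%. Three waves: ICC 0.075, DE = 2.05, R = 1.525, 1.96/√1.525 = 1.587, type I error 11.2%.

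| Type I error of a person-level model at ICC | 0.01 | 0.02 | 0.05 | 0.10 |
|---|---|---|---|---|
| Single wave, all attend (formula) | 5.8% | 6.6% | 9.2% | 13.3% |
| Single wave, 10 of 15 attend (formula) | 5.3% | 5.7% | 6.8% | 8.6% |
| Three waves, all attend (formula) | 6.2% | 7.5% | 11.2% | 17.1% |
| Three waves, all attend (simulated GEE by participant) | 6.4% | 7.4% | 11.5% | 17.7% |
| Three waves, 10 of 15 attend (simulated GEE by participant) | 5.7% | 6.1% | 7.8% | 10.4% |

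The simulated rows use 20,000 trials per cell. A separate simulation with a different data-generating model gave 5.9%, 7.5%, 10.8% and 16.7% for three waves with full attendance. A logistic model with a participant random intercept gave 7.5%, 10.6% and 16.5% at ICC 0.02, 0.05 and 0.10; these rest on 604 to 751 trials each, with a Monte Carlo error of roughly 0.6 to 1.4 points.

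**Standard error.** The true value exceeds the model's by √1.07 = 1.03 to √1.70 = 1.30 (single wave), or √1.105 = 1.05 to √2.05 = 1.43 (three waves).

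**Sensitivity.**
- At ICC 0.05 with three waves, moving r from 0.3 to 0.7 takes the formula value from 12.8% to 10.2%.
- If the control arm were also clustered, R = DE, and the single-wave values become 6.6%, 8.3%, 13.3% and 20.6%.
- At ICC 0 the simulated level was 4.8% to 5.3%.

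**The case against.** **The model is unspecified rather than wrong.** The document is a protocol summary with one sentence on Aim 1. A multilevel model with a group effect would fit its words. That is true, but a reader applying the sentence as usually understood would omit the group. Leaving the choice until the data are seen, with 10 groups and results that depend on the reference distribution, puts discretion into the primary result.

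**The evidence for correlation is indirect.** The remark on learning from other members concerns coping skills, which are secondary outcomes. The protocol does not say that facilitators differ between groups, and review of recorded sessions for fidelity should limit divergence. All of this bears on how large the ICC may be. None of it shows that the ICC is zero.

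**The largest figures assume a group effect that lasts to month 12.** This stands. Suppose the effect halves at each wave (multipliers 1, 0.5, 0.25; mean 0.583, squared 0.340). The ICC of the three-wave mean is then 0.340 × ICC/(2/3). Type I error at ICC 0.01, 0.02, 0.05 and 0.10 falls to 5.4%, 5.8%, 7.1% and 9.3% with full attendance. With 10 of 15 attending it is 5.2%, 5.4%, 5.9% and 6.8%. The inflation shrinks but keeps its direction.

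**The null is particular.** If the programme changes nobody's outcome, group delivery adds no correlation and the level holds. This is correct, and it limits the type I error claim. It does not rescue the confidence intervals when effects differ between groups.

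**The remedy is only partly tested.** The simulations had no covariates and no dropout, and did not cover the mediation or moderator models. This stands as a limit on the evidence for those parts.

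**Conclusion.** The concern holds. A trial that randomizes individuals and treats one arm in groups has a primary model that, as stated, leaves the groups out. At any positive within-group correlation the standard errors for both primary outcomes are too small.

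The size cannot be fixed from the documents, because the ICC, alpha, attendance and persistence of the group effect are all unknown. Over the assumptions examined, a nominal 5% test runs from barely above 5% (low ICC, partial attendance, fading effect) to about 17% or 18% (ICC 0.10, full attendance, persistent effect). The upper values are not a forecast. The direction is firm, the trial's own model would not reveal the problem, and a method that holds the level is available at modest cost, so this should be corrected before the primary analysis.

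**What to change.** In section 5, specify Aim 1 as a partially nested analysis:

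- **Primary model.** Logistic GEE with an independence working correlation, clustered on assigned intervention group, each control participant forming their own cluster. Clustering on group also covers the repeated measures within a person. Name the small-sample correction (K/(K − 1) for K groups was the one tested) and use Satterthwaite degrees of freedom reflecting the 10 groups. Simulated type I error was 4.7% to 5.2% for ICC 0 to 0.10, with full or partial attendance.
- **Sensitivity model.** Mixed logistic regression with participant and intervention-group random intercepts. Keep small-sample degrees of freedom even when the group variance is estimated at zero, which happened in 36% of fits at ICC 0.02 and 14% at 0.05. With a normal reference this model gave 6.1% to 7.0% at ICC 0.02 to 0.10; with t on 9 df it was conservative, at 3.0% to 4.1%.
- **Group membership.** Define group as the assigned group, recorded at assignment, including for those who never attend.
- **Control arm.** Reconcile the two descriptions in section 3. Add a control-group effect only if control groups actually meet as units.
- **Other models.** Carry the same structure into the Aim 2 mediation and the moderator analyses, and state the assumed ICC.

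**Cost.** SAP wording and one recorded variable, plus wider intervals. Take an effect with 80% power under independence (single wave) and df = (DE + 1)²/(DE²/9 + 1/149):

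| ICC | 0 | 0.02 | 0.05 |
|---|---|---|---|
| Power, corrected analysis | 77.7% | 71.6% | 63.5% |
| Interval wider by | 4% | 12% | 23% |

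At ICC 0.05 most of the loss is the clustering itself: power is 67.4% with the correct standard error and a normal reference. The degrees-of-freedom correction accounts for about 2 to 4 points across this range.

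### Mediation is estimated only for secondary outcomes with a significant intervention effect, so coping, the named mechanism, may get no mediation estimate, or one that is too large on average

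*Combined protocol and SAP*

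**What the plan says.** Section 2 (Objectives) sets as its second objective to "examine mechanisms of intervention effects on regular HIV testing and PrEP use, including more effective coping". It attaches no significance condition.

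Section 5 (Statistical Analysis, Aim 2) adds one. The candidates are introduced as "For secondary outcomes (e.g., coping, internalize stigma", that is, by example, and the analysis goes ahead only for those "on which the coping intervention shows significant effects, to test mediation we will compare" two versions of the Aim 1 model. Version (a) adds the mediator at baseline; version (b) also adds it after the intervention. The result examined is whether this "decreases the coefficient for intervention effects on the outcome relative to the corresponding coefficient from (a").

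The level at which an effect counts as significant is not defined. The only threshold in Section 5 is p < .10, and that is for choosing covariates. The documents give no interval for the mediated effect, no expected effect on coping and no mediation analysis free of the condition.

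**The concern.** A significance test decides whether a mediator is analysed, and the same participants then supply the mediation estimate. This has two consequences.

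- **Missing estimate.** A real effect on coping that falls short of significance removes coping from the model comparison. Objective 2 then has no mediation estimate for the one mechanism that it names.
- **Biased estimate.** Samples in which the effect on coping came out large by chance are more likely to pass. The fall in the coefficient from (a) to (b) grows with the observed effect on coping, so it too is too large on average among the samples that pass.

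A reader planning a later trial, or judging how the intervention works, would see either no figure for coping or one with upward bias on average, and could not tell how much bias.

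**Working it through.** **Inputs from the documents.** Section 3 (Study Design) states: "We will conduct 10 intervention groups and 10 standard of care control groups of about 15 participants each (n=300"). Check: (10 + 10) × 15 = 300, about 150 per arm. No power calculation is given, so none can be reproduced.

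**Assumptions.** Two-sided 5% level for the significance condition; correlation of 0.5 between the baseline and later mediator measures; 300 men analysed, or 255 (15% loss: 300 × 0.85); no clustering; true effect on the mediator d from 0.15 to 0.50 SD. None of these is stated in the documents.

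**Step 1: standard error of the baseline-adjusted standardized difference.** SE = 2 × √(1 − 0.5²) / √n.

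- n = 300: 2 × 0.866 / 17.32 = 0.100
- n = 255: 2 × 0.866 / 15.97 = 0.108

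**Step 2: chance of passing.** With λ = d/SE and c = 1.96, P = Φ(λ − c) + Φ(−λ − c).

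**Step 3: mean estimate given a pass, relative to the truth.** Ratio = 1 + [φ(c − λ) − φ(c + λ)] / (λP).

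Example, d = 0.20 and n = 300: λ = 2.00, P = 0.516, ratio = 1 + (0.3986 − 0.0002) / (2.00 × 0.516) = 1.39.

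| True effect (SD) | Passes, n = 300 / 255 | Mean inflation given a pass, n = 300 / 255 |
|---|---|---|
| 0.15 | 32% / 28% | 74% / 86% |
| 0.20 | 52% / 45% | 39% / 47% |
| 0.30 | 85% / 79% | 9% / 13% |
| 0.40 | 98% / 96% | 1% / 3% |
| 0.50 | above 99% / above 99% | under 1% / under 1% |

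The smallest significant difference is 1.96 × 0.100 = 0.196 SD at n = 300. If the true effect is below that, every passing estimate in the right direction is too large. Above it, inflation holds only on average.

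**Step 4: less favourable assumptions.** With no gain from the baseline measure, SE = √(2/n per arm). At 150 per arm, coping is left out in 59%, 26%, 7% and 1% of trials at d = 0.2, 0.3, 0.4 and 0.5, and the mean ratios are 1.55, 1.17, 1.04 and 1.01. At 120 per arm (20% loss), with an assumed intraclass correlation of 0.05 in groups of 12 (design effect 1 + 11 × 0.05 = 1.55), it is left out in 76%, 54%, 30% and 13%, with ratios 2.05, 1.46, 1.20 and 1.08.

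**Step 5: does the bias reach the planned measure?** Models (a) and (b) were simulated at 150 per arm with an assumed mediator-outcome log-odds of 0.5 per SD (3,000 trials per scenario, no clustering, no gain from baseline). The mean fall in the coefficient among passing trials, relative to all trials, was 1.47, 1.14, 1.03 and 1.00 at d = 0.2, 0.3, 0.4 and 0.5. It does carry through, slightly reduced.

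**Step 6: power to detect mediation.** In the same simulations, the chance that an interval for the indirect effect excludes zero was 37.5% without the condition and 36.4% with it at d = 0.2, 69.5% and 68.6% at 0.3, and 88.1% and 87.7% at 0.4.

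**The case against.** The case for the plan is that an intervention with no effect on a mediator leaves nothing to mediate, and that requiring that effect first is a recognised sequential approach. Step 6 supports part of this: the condition costs about one percentage point of power, or less, because a weak effect on coping rarely gives a clear indirect effect. That stands, so lost power is not the complaint. But a non-significant effect is not an absent one. At 0.20 SD under the main assumptions, a real effect misses about half the time.

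Four stronger readings are tempting, and none is supported.

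- *The trial would say nothing about coping.* Section 5 hypothesizes "improved coping with stigma (e.g., reduced internalized stigma"), and the condition cannot be applied without estimating that effect. Only the model comparison is lost.
- *Every passing estimate is inflated.* The inflation is an average, and it is negligible at 0.4 to 0.5 SD under the main assumptions.
- *The share of the effect explained is exaggerated.* The plan computes no share, and selection also raises the total effect. In simulations at d = 0.2 (n = 300, correlation 0.5, log-odds 0.5 per SD), the share went from 1.10 in all trials to 1.08 in passing trials under full mediation, but from 0.22 to 0.30 with an assumed direct log-odds of 0.3. It depends on the scenario.
- *The condition lets unaffected outcomes in by chance.* It does, but removing it admits every listed mediator, unaffected ones included. This is no argument for the change. Nor are the candidates chosen by results alone: Section 5 speaks of hypothesized mediators and names two.

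**Conclusion.** The point holds as a matter of selective reporting and biased estimation in a secondary aim. Followed exactly, the plan can leave objective 2 without a mediation estimate for coping, or with one that is too large on average.

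The size turns on the unknown true effect. It is substantial at 0.15 to 0.20 SD, modest at 0.30 SD and close to nil from 0.40 SD upward under the main assumptions; loss to follow-up and clustering within groups would make it larger. The calculation uses a single follow-up comparison, whereas the trial has three follow-up waves, which could move the figures either way. The documents give nothing that places the trial within this range. The primary Aim 1 inference is not affected.

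**What to change.** In Section 5, Aim 2, delete the condition that the intervention "shows significant effects" on the secondary outcome. Prespecify a closed, short list of mediators, with coping first and internalized stigma next; both are already named there. For each, report the mediated effect with a confidence interval, whatever the significance of the intervention's effect on it.

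The cost is SAP wording only; no new data, visits or participants are needed. The downside is that a few more mediated effects are reported, some with wide intervals.
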